8.4.2 Method of Detecting AEs, SAEs, and Other Reportable Safety Events

Care will be taken not to introduce bias when detecting AEs and/or SAEs and other reportable safety events. Open-ended and nonleading verbal questioning of the participant is the preferred method to inquire about AE occurrence.

8.4.3 Follow-up of AE, SAE, and Other Reportable Safety Event Information

After the initial AE/SAE report, the investigator is required to proactively follow each participant at subsequent visits/contacts. All AEs, SAEs, and other reportable safety events, including pregnancy and exposure during breastfeeding, ECIs, cancer, and overdose will be followed until resolution, stabilization, until the event is otherwise explained, or the

participant is lost to follow-up (as defined in Section 7.3). In addition, the investigator will make every attempt to follow all nonserious AEs that occur in randomized participants for outcome. Further information on follow-up procedures is given in Appendix 3.

8.4.4 Regulatory Reporting Requirements for SAE

Prompt notification (within 24 hours) by the investigator to the Sponsor of SAE is essential so that legal obligations and ethical responsibilities towards the safety of participants and the safety of a study intervention under clinical investigation are met.

The Sponsor has a legal responsibility to notify both the local regulatory authority and other regulatory agencies about the safety of a study intervention under clinical investigation. The Sponsor will comply with country-specific regulatory requirements and global laws and regulations relating to safety reporting to regulatory authorities, IRB/IECs, and investigators.

Investigator safety reports must be prepared for SUSARs according to local regulatory requirements and Sponsor policy and forwarded to investigators as necessary.

An investigator who receives an investigator safety report describing an SAE or other specific safety information (eg, summary or listing of SAE) from the Sponsor will file it along with the IB and will notify the IRB/IEC, if appropriate according to local requirements.

8.4.5 Pregnancy and Exposure During Breastfeeding

Information in this section is not applicable since participants are infants.

8.4.6 Disease-related Events and/or Disease-related Outcomes Not Qualifying as AEs or SAEs

Not applicable to this study.

8.4.7 Events of Clinical Interest

Selected nonserious and SAEs are also known as ECIs and must be reported to the Sponsor.

Events of clinical interest for this study include:

- a. Intussusception: Any cases of intussusception during the entire study should be immediately reported to Sponsor (see Section 8.4.1 for safety reporting requirement).

8.5 Treatment of Overdose

In this study, an overdose is defined as receiving more than one dose of V260 within a 12-day period. Any overdose should be reported to Sponsor (see Section 8.4.1 for safety reporting requirement).

Sponsor does not recommend specific treatment for an overdose.

8.6 Pharmacokinetics

PK parameters will not be evaluated in this study.

8.7 Pharmacodynamics

Pharmacodynamic parameters will not be evaluated in this study.

8.8 Biomarkers

Biomarkers are not evaluated in this study.

8.9 Future Biomedical Research Sample Collection

Future biomedical research samples will not be collected in this study.

8.10 Medical Resource Utilization and Health Economics

Medical Resource Utilization and Health Economics are not evaluated in this study.

8.11 Visit Requirements

Visit requirements are outlined in Section 1.3. Specific procedure-related details are provided in Section 8.

8.11.1 Screening

At Visit 1, if participant has a fever (axillary temperature $\geq 37.5^{\circ}\text{C}$ or equivalent) within the 24-hour period prior to vaccination, screening visit may be rescheduled after the fever has resolved.

Screening procedures may not be performed on the same day of ICF, but screening or rescreening visit should be on the same day as randomization. Screening procedures may be repeated after consultation with the Sponsor.

8.11.2 Vaccination Visit

This section summarizes prerequisites for visits with study vaccinations. Deviations from these prerequisites require consultation between the investigator and the Sponsor and written documentation of the collaborative decision.

See the inclusion/exclusion criteria for specific restrictions at Visit 1 (see Section 5.1 and Section 5.2). At the subsequent vaccination visits, study personnel should verify by questioning the participant and/or by examination that:

1. The participant has not had a fever (defined as an axillary temperature of $\geq 37.5^{\circ}\text{C}$ or equivalent) within the 24-hour period prior to each vaccination visit.

2. The participant has not received any systemic (oral, intravenous or intramuscular) corticosteroids within 2 weeks (14 days) prior to each vaccination visit.
3. The participant has not received a non-study inactivated or recombinant vaccine within 2 weeks (14 days) prior to each vaccination visit.
4. The participant has not received a non-study live vaccine within 4 weeks (28 days) prior to each vaccination visit.

If the participant does not meet the requirements #1 or #2 listed above during study, the vaccination visit should be rescheduled as soon as possible.

It is recommended other routine vaccines be administered on the same day as V260 or IPV. If other routine vaccines are to be administered on different day of study vaccines, the interval between non-study and study vaccines should meet the requirements #3 and #4 listed above or may be determined in accordance with institutional guidance (see Section 8.1.8.1).

8.11.3 Discontinued Participants Continuing to be Monitored in the Study

Participants who discontinue study vaccinations but continue in the study may attend study visits per the SoA (Section 1.3). However, post-vaccination serum samples will not be collected from participants who have not completed the 3-dose regimen of study vaccination.

9 STATISTICAL ANALYSIS PLAN

This section outlines the statistical analysis strategy and procedures for the study. If, after the study has begun, but prior to any final database lock, changes are made to primary and/or key secondary hypotheses, or the statistical methods related to those hypotheses, then the protocol will be amended (consistent with ICH Guideline E-9). Changes to exploratory or other non-confirmatory analyses made after the protocol has been finalized, but prior to final database lock, will be documented in a supplemental SAP (sSAP) and referenced in the Clinical Study Report (CSR) for the study. Post hoc exploratory analyses will be clearly identified in the CSR.

9.1 Statistical Analysis Plan Summary

Key elements of the statistical analysis plan are summarized below; the comprehensive plan is provided in Sections 9.2-9.12.

Study Design Overview	A Phase 3 Randomized, Open-Label, Clinical Trial to Study the Immunogenicity and Safety of Concomitant and Non-Concomitant Administration of V260 and Inactivated Poliomyelitis Vaccine (IPV) in Chinese Healthy Infants
Treatment Assignment	Participants will be randomly assigned in a 1:1 ratio to receive V260 and IPV in a concomitant-use or staggered-use schedule
Analysis Populations	Immunogenicity: Per-Protocol Immunogenicity (PPI) population Safety: All Participants as Treated (APaT) population

Primary Endpoint(s)	Immunogenicity: 
 Neutralizing antibody seroconversion percentages to each of poliovirus types 1, 2, and 3 at 1 month post dose 3 of IPV
Secondary Endpoints	Immunogenicity: 
 Neutralizing antibody geometric mean titers (GMTs) to each of poliovirus types 1, 2, and 3 at 1 month post dose 3 of IPV Proportions of participants with neutralizing antibody titer $\geq 1:8$ and $\geq 1:64$ at 1 month post dose 3 of IPV for each of poliovirus types 1, 2, and 3 Safety: 
 Proportions of participants with solicited injection-site AEs (erythema, swelling, induration, and pain at the injection-site of IPV) from Day 1 through Day 7 following any vaccination of IPV Proportions of participants with solicited systemic AEs (diarrhea and/or vomiting) from Day 1 through Day 7 following any vaccination of V260 and/or IPV Proportions of participants with SAEs from Day 1 through end of study
Statistical Methods for Key Immunogenicity Analyses	For the primary hypothesis, concomitant-use group will be considered non-inferior to staggered-use group if the lower bound of the two-sided 95% confidence interval (CI) for the difference in seroconversion percentage (concomitant-use group minus staggered-use group) is greater than -10% for each poliovirus type.
Statistical Methods for Key Safety Analyses	All safety data will be summarized as frequencies and percentages for the two vaccination groups.
Interim Analyses	No interim analysis is planned.
Multiplicity	Since success is required on all 3 poliovirus types for the primary hypothesis, no multiplicity adjustment will be made for the multiple tests.
Sample Size and Power	The planned sample size is 400 participants. For the seroconversion percentage to each of poliovirus types 1, 2, and 3 at 1 month post dose 3, the study has approximately an overall 90.0% power to demonstrate that the concomitant-use group is non-inferior to the staggered-use group at an overall one-sided 2.5% alpha-level, if the underlying treatment difference is 0 percentage points.

9.2 Responsibility for Analyses/In-house Blinding

The statistical analysis of the data obtained from this study will be the responsibility of the Clinical Biostatistics department of the SPONSOR.

This study is being conducted as a randomized, open-label study, i.e., participants, investigators, and SPONSOR personnel will be aware of participant treatment assignments after each participant is enrolled and treatment is assigned.

The Clinical Biostatistics department will generate the randomized allocation schedule(s) for study intervention assignment. Randomization will be implemented using an IRT.

9.3 Hypotheses/Estimation

Objectives and hypotheses of the study are stated in Section 3.

9.4 Analysis Endpoints

Immunogenicity and safety endpoints that will be evaluated or summarized are listed below.

9.4.1 Immunogenicity Endpoints

A description of immunogenicity assessments is presented in Section 4.2.1.1.

The primary immunogenicity analysis endpoints are neutralizing antibody seroconversion percentages to each of poliovirus types 1, 2, and 3 at 1 month post dose 3 of IPV. The seroconversion is defined as antibody titer $\geq 1:8$ post-vaccination in baseline seronegative participants or ≥ 4 -fold increase in titer post-vaccination in baseline seropositive participants. The cut-off value determining baseline seropositivity is 1:8 for all 3 poliovirus types. Neutralizing antibodies to poliovirus types 1, 2, and 3 will be measured by the laboratory of NIFDC.

The secondary immunogenicity analysis endpoints include:

- Neutralizing antibody GMTs to each of poliovirus types 1, 2, and 3 at 1 month post dose 3 of IPV.
- Proportions of participants with neutralizing antibody titer $\geq 1:8$ and $\geq 1:64$ at 1 month post dose 3 of IPV for each of poliovirus types 1, 2, and 3.

The exploratory immunogenicity analysis endpoints include:

- Proportions of participants with ≥ 3 -fold increase in anti-rotavirus type-specific IgA titer post-vaccination from baseline to serotypes G1, G2, G3, G4, and P1A[8] at 1 month post dose 3 of V260.
- Anti-rotavirus type-specific IgA GMTs to serotypes G1, G2, G3, G4, and P1A[8] at 1 month post dose 3 of V260.

9.4.2 Safety Endpoints

A description of safety measures is presented in Section 4.2.1.2 and Section 8.3. The analysis of safety results is described in Section 9.6.2.

Safety and tolerability will be assessed by clinical review of all relevant parameters including AEs and post-vaccination temperature measurements following V260 and/or IPV.

The safety analysis endpoints include:

- Proportions of participants with solicited injection-site AEs (erythema, swelling, induration, and pain at the injection-site of IPV) from Day 1 through Day 7 post-vaccination of IPV in the two vaccination groups
- Proportions of participants with solicited systemic AEs (diarrhea and/or vomiting) from Day 1 through Day 7 post-vaccination of V260 and IPV in the concomitant-use group, and from Day 1 through Day 7 post-vaccination of V260 plus from Day 1 through Day 7 post-vaccination of IPV in the staggered-use group
- Proportions of participants with any injection-site AEs from Day 1 through Day 15 post-vaccination of V260 and IPV in the concomitant-use group, and from Day 1 through Day 15 post-vaccination of IPV in the staggered-use group
- Proportions of participants with any systemic AEs from Day 1 through Day 30 post-vaccination of V260 and IPV in the concomitant-use group, and from Day 1 through Day 15 post-vaccination of V260 plus from Day 1 through Day 15 post-vaccination of IPV in the staggered-use group
- Proportions of participants with any vaccine-related injection-site AEs from Day 1 through Day 15 post-vaccination of V260 and IPV in the concomitant-use group, and from Day 1 through Day 15 post-vaccination of IPV in the staggered-use group
- Proportions of participants with any vaccine-related systemic AEs from Day 1 through Day 30 post-vaccination of V260 and IPV in the concomitant-use group, and from Day 1 through Day 15 post-vaccination of V260 plus from Day 1 through Day 15 post-vaccination of IPV in the staggered-use group
- Proportion of participants with any SAE, any AE which is both vaccine-related and serious, any AE resulting in discontinuation, and proportion of participants who died, proportion of participants with intussusception during the entire study period in the two vaccination groups
- Proportions of participants with maximum temperature measurements from Day 1 through Day 7 post-vaccination of V260 and IPV in the concomitant-use group, and Day 1 through Day 7 post-vaccination of V260 plus Day 1 through Day 7 post-vaccination of IPV in the staggered-use group

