8.1.8.1 Timing of Dose Administration

In the concomitant-use group, each participant will receive 1 dose of V260 and IPV concomitantly at Visit 2, 4, and 6, respectively. In the staggered-use group, each participant will receive 1 dose of V260 at Visit 1, 3, and 5, respectively, and 1 dose of IPV at Visit 2, 4, and 6, respectively. See the SoA (Section 1.3) for the protocol pre-specified time windows of these vaccination visits. Missed study vaccination doses within the visit window should be completed as soon as possible.

The first dose of V260 should be given by 12 weeks of age (84 days of age) and the third dose of V260 should be given by 32 weeks of age (224 days of age). The minimum and maximum interval between each dose of V260 should be 4 weeks (28 days) and 10 weeks (70 days), respectively.

The minimum age for the first dose of IPV should be 2 months of age. The minimum interval between each dose of IPV should be 1 month (30 days).

In the staggered-use group, the minimum interval between V260 and subsequent IPV should be 15 days.

Administration of approved routine pediatric vaccine (excluding rotavirus vaccine and polio vaccines other than study vaccines) is allowed in the study. It is recommended other routine vaccines (including EPI and non-EPI vaccines) be administered on the same day as V260 or IPV.

If other routine vaccines are to be administered concomitantly with V260, V260 should be administered before administration of other vaccines to minimize crying and the chance of the participant spitting up V260.

If other routine vaccines are to be administered on different day of study vaccines, the interval between non-study and study vaccines should meet the prerequisites of vaccination visit (Section 8.11.2) or may be determined in accordance with the routine practice of study institution.

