9.6.2 Statistical Methods for Safety Analyses

Safety and tolerability will be assessed by clinical review of all relevant parameters including AEs and post-vaccination temperature measurements.

An overall assessment of adverse events will be summarized for each group by dose period (dose period is defined in [Table 4](#)) and across all dose periods.

Table 4 Each Group by Dose Period

Dose Period	Concomitant-Use Group (Vaccine administered)	Staggered-Use Group (Vaccine administered)
1	Visit 2 (V260 + IPV)	Visit 1 (V260)
	Visit 3	Visit 2 (IPV)
2	Visit 4 (V260 + IPV)	Visit 3 (V260)
	Visit 5	Visit 4 (IPV)
3	Visit 6 (V260 + IPV)	Visit 5 (V260)
	Visit 7	Visit 6 (IPV)

Summary statistics, counts and percentage without confidence interval, will be provided by group. Proportions of participants with solicited injection-site AEs (following vaccination of IPV), solicited systemic AEs within 7 days following study vaccination will be given. Maximum axillary temperatures recorded on the VRC from Day 1 through Day 7 post-vaccination will be summarized. Table 5 shows the safety endpoints that will be summarized.

Table 5 Analysis Strategy for Safety Parameters

Safety Endpoints	Time Period	Descriptive Statistics
Solicited Injection-Site AEs	Days 1-7 post-vaccination of V260 and IPV in the concomitant-use group, and Days 1-7 post-vaccination of IPV in the staggered-use group, across all dose periods and by dose period	X
Solicited Systemic AEs	Days 1-7 post-vaccination of V260 and IPV in the concomitant-use group, and Days 1-7 post-vaccination of V260 plus Days 1-7 post-vaccination of IPV in the staggered-use group, across all dose periods and by dose period	X
Maximum Axillary Temperature	Days 1-7 post-vaccination of V260 and IPV in the concomitant-use group, and Days 1-7 post-vaccination of V260 plus Days 1-7 post-vaccination of IPV in the staggered-use group, across all dose periods and by dose period	X
Any Injection-Site AEs	Days 1-15 post-vaccination of V260 and IPV in the concomitant-use group, and Days 1-15 post-vaccination of IPV in the staggered-use group, across all dose periods and by dose period	X
Any Systemic AEs	Days 1-30 post-vaccination of V260 and IPV in the concomitant-use group, and Days 1-15 post-vaccination of V260 plus Days 1-15 post-vaccination of IPV in the staggered-use group, across all dose periods and by dose period	X

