Any Vaccine-related Injection-Site AEs	Days 1-15 post-vaccination of V260 and IPV in the concomitant-use group, and Days 1-15 post-vaccination of IPV in the staggered-use group, across all dose periods and by dose period	X
Any Vaccine-related Systemic AEs	Days 1-30 post-vaccination of V260 and IPV in the concomitant-use group, and Days 1-15 post-vaccination of V260 plus Days 1-15 post-vaccination of IPV in the staggered-use group, across all dose periods and by dose period	X
Discontinuation due to any AE	Entire Study Period by Vaccination Group	X
Any Serious AEs including Intussusception	Entire Study Period by Vaccination Group	X

X = results will be provided.

To assess the severity of adverse events, both Sponsor's criteria (see "Assessment of Intensity/Toxicity" in Section 10.3 - Appendix 3) and China Regulatory Agency's criteria (see Section 10.7 - Appendix 7: Country-specific Requirements) will be applied. The incidence of greatest adverse event severity reported by a participant based on both the two criteria will be tabulated for: all injection-site AEs and all systemic AEs across all dose periods.

For the across dose-period summaries and analyses, if the same AE occurs multiple times across dose periods, the AE will be counted once. In order to evaluate any additive safety issues for the concomitant use of V260 and IPV compared to the staggered use of these vaccines, the following summaries will also be provided: Frequencies and percentages of the solicited systemic AEs during Days 1 to 7 after V260 concomitant with IPV in the concomitant-use group, during Days 1 to 7 after V260 alone in the staggered-use group, and during Days 1 to 7 after IPV alone in the staggered-use group.

Any injection-site AEs and vaccine-related injection-site AEs during Days 1 to 30 post-vaccination of V260 and IPV in the concomitant-use group will be summarized separately.

Any reportable safety events collected between Visit 1 and 2 in the concomitant-use group will be listed separately.

For serious adverse events observed during the study, including intussusception, a detailed description will be included in the CSR.

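### Every planned maximum-temperature summary compares windows of unequal length (21 vs 42 days, or 7 vs 14 by dose period), and the equal-window Days 1-7 split planned for solicited systemic AEs is not extended to temperature

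*Combined protocol and SAP*

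**What the plan says.** Section 9.4.2 lists, among the safety endpoints, "Proportions of participants with maximum temperature measurements from Day 1 through Day 7 post-vaccination of V260 and IPV in the concomitant-use group", and for the other group "Day 1 through Day 7 post-vaccination of V260 plus Day 1 through Day 7 post-vaccination of IPV in the staggered-use group". The Maximum Axillary Temperature row of Table 5 (Section 9.6.2) uses the same windows: "Days 1-7 post-vaccination of V260 and IPV in the concomitant-use group, and Days 1-7 post-vaccination of V260 plus Days 1-7 post-vaccination of IPV". It asks for them both across all dose periods and by dose period. Table 4 places one joint vaccination visit in each concomitant-use dose period and two vaccination visits (V260, then IPV) in each staggered-use dose period. The text of Section 9.6.2 adds only "Maximum axillary temperatures recorded on the VRC from Day 1 through Day 7 post-vaccination will be summarized".

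The same section plans one further display. Its stated aim is "In order to evaluate any additive safety issues for the concomitant use of V260 and IPV compared to the staggered use of these vaccines", and its content is "Frequencies and percentages of the solicited systemic AEs during Days 1 to 7 after V260 concomitant with IPV in the concomitant-use group", set beside Days 1-7 after V260 alone and Days 1-7 after IPV alone in the staggered-use group. Section 9.4.2 limits solicited systemic AEs to diarrhea and/or vomiting, so temperature falls outside this display.

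Section 9.6.2 presents safety as counts and percentages without confidence intervals. Temperature is not among the primary or secondary endpoints in Section 9.1.

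**The concern.** A maximum taken over more days can only stay the same or rise. The staggered-use group is read over twice as many post-vaccination days, so background fever from any cause has twice the opportunity to appear there. If co-administration produced more fever than the two vaccines given separately would predict, that excess could be offset by the extra background in the staggered-use column. The two groups would then look alike.

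The plan already recognises this kind of question, since it splits solicited systemic AEs into three equal-window columns to look for additive effects. Temperature is the other Days 1-7 systemic measure with the same pooled windows in Table 5, but it gets no such split. At stake is how the safety tables are read. No test, margin or stopping rule depends on them.

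**Working it through.** The documents state no fever rate, sample size or power for temperature, so there is no figure to reproduce. The window counts come from the documents. Every rate below is an assumption.

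**Window lengths**
- Vaccination visits (Section 8.1.8.1): 3 in the concomitant-use group (Visits 2, 4, 6) and 6 in the staggered-use group (Visits 1 to 6).
- Across dose periods: 3 × 7 = 21 days vs 6 × 7 = 42 days.
- By dose period (Table 4): 1 × 7 = 7 vs 2 × 7 = 14 days. The by-period rows keep the 1:2 ratio.
- The 42 days are distinct. Section 8.1.8.1 says "In the staggered-use group, the minimum interval between V260 and subsequent IPV should be 15 days", and the visit windows in Section 1.3 put each later V260 dose at least 15 days after the preceding IPV dose.
- The three-column split, if applied to temperature: 7 vs 7 vs 7 days per dose, or 21 vs 21 vs 21 over three doses.

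**Background only, no vaccine effect.** Let r be the probability of a fever reading in a 7-day window. With independent windows the pooled figures are 1−(1−r)³ vs 1−(1−r)⁶. For within-infant correlation ρ, use a beta-binomial with α = r(1−ρ)/ρ and β = (1−r)(1−ρ)/ρ, so that P(at least one in k windows) = 1 − B(α, β+k)/B(α, β), with k = 3 vs 6. At r = 5%:

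| ρ | Concomitant | Staggered |
|---|---|---|
| 0 | 14.3% | 26.5% |
| 0.2 | 11.8% | 18.4% |
| 0.4 | 9.8% | 13.5% |

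With independent windows the split would show 14.3% in all three columns.

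**How large an excess the pooled table could hide.** Let b be the background per window and v the effect per vaccine.
- Single-vaccine window: s = 1−(1−b)(1−v).
- Joint window without interaction: j = 1−(1−b)(1−v)².
- With independent windows, the pooled figures are equal when the joint window equals 1−(1−s)². The hidden excess per joint window is then 1−(1−s)²−j = b(1−b)(1−v)².

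At b = 5%, v = 2.5%: s = 7.375% and j = 9.691%. The joint window that equalises the pooled figures is 14.206%, so the hidden excess is 4.5 points.
- Pooled: 1−(1−0.14206)³ = 36.9% vs 1−(1−0.07375)⁶ = 36.9%.
- Split: 36.9% vs 20.5% vs 20.5%, where 20.5% = 1−(1−0.07375)³.
- Split without interaction: 26.3% vs 20.5% vs 20.5%, where 26.3% = 1−(1−0.09691)³.

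Solving the beta-binomial for the same case, the equalising joint window is 11.62% at ρ = 0.2 (hidden excess 1.9 points) and 10.24% at ρ = 0.4 (0.6 points). At b = 1%, v = 2.5% the hidden excess is 0.9 points if independent and negative (nothing hidden) at ρ = 0.2. At b = 0 with independent windows it is zero.

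**Cases that run the other way.** These use the same model with no interaction:
- b = 2%, v = 5%, ρ = 0.2: pooled 25.9% concomitant vs 24.6% staggered.
- b = 5%, v = 5%, ρ = 0.4: pooled 26.4% vs 25.0%.

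Here the pooled table makes concomitant use look slightly worse.

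**The split is not neutral either.** At b = 0, v = 5%, independent windows and no interaction, pooled reads 26.5% vs 26.5%, while the split reads 26.5% vs 14.3% vs 14.3%. One column reflects two vaccines and the others reflect one.

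**The case against.** The strongest reply is that nothing in the plan is inconsistent. Section 9.4.2 and Table 5 agree and state each group's windows openly, and a whole-regimen summary is a legitimate choice. The split is an extra display for one endpoint, and nothing commits the sponsor to repeating it. This stands: the point is a missed opportunity, not an error.

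A reader might infer that the temperature table is bound to favour concomitant use. The documents do not support that. They give neither a background rate nor a within-infant correlation, and the two reverse cases above show that the sign can change. The 4.5-point illustration is the independence case and shrinks quickly with correlation. With 200 infants per group, the standard error of a difference near 10% is √(2 × 0.1 × 0.9/200) = 3.0 points, so the smaller hidden excesses per window lie below sampling noise.

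A reader might also infer that fever goes otherwise unexamined. That would be wrong too. Any systemic AEs and vaccine-related systemic AEs cover 3 × 30 = 90 days in the concomitant-use group. In the staggered-use group they are counted "from Day 1 through Day 15 post-vaccination of V260 plus from Day 1 through Day 15 post-vaccination of IPV in the staggered-use group", which is 6 × 15 = 90 days. Section 8.3.4 requires suspected fever after Day 7 to be measured and recorded. Section 9.6.2 tabulates greatest AE severity also under the China criteria, which grade axillary fever (Table 9). These displays pool fever with other systemic events, and none shows maximum temperature over equal windows, so they narrow the gap without closing it.

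Finally, the split compares two vaccines with one. That stands, and it is why the pooled table should be kept.

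**Conclusion.** The point holds as a limited one. All planned maximum-temperature summaries use windows in a 1:2 ratio, and the equal-window display that serves the plan's own additive-safety aim omits temperature. The day counts are certain.

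The consequence is conditional. To the extent that raised temperatures are background, the staggered-use figure is inflated and an excess beyond the two separate effects can be hidden. Under the assumed b = 5% and v = 2.5%, that excess is between 0.6 and 4.5 points per joint window for correlations from 0.4 down to 0. Under other assumptions it is nil, or the distortion reverses. The documents fix neither its size nor the net direction. The analysis is descriptive and the primary non-inferiority hypothesis is unaffected. Severity: a change that could be made because it is cheap.

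**What to change.** In Section 9.6.2 and Table 5, extend the three-column Days 1-7 summary (after V260 with IPV, after V260 alone, after IPV alone) to maximum axillary temperature. Use as denominator the infants with at least one reading in that column's windows, in line with the temperature rule in Section 9.5.2.

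Keep the pooled whole-regimen summary, with a footnote that it rests on 21 vs 42 observed days (7 vs 14 by dose period). Add a note that the split sets two vaccines against one, so the two displays should be read together.

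The cost is one sentence, one table shell and a footnote. Daily temperatures for Days 1-7 after each vaccination are already recorded on the report card (Section 8.3.4). Because the analysis is non-confirmatory, Section 9 allows the change to be documented in the supplemental SAP before database lock, without a protocol amendment. Specifying it then also avoids a later temperature split that the study report would have to identify as post hoc.
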